6.2.2 Handling, Storage and Accountability

- The investigator or designee must confirm appropriate temperature conditions have been maintained during transit for all IP received and any discrepancies are reported and resolved before use of the IP.
- Only participants enrolled in the study may receive IP and only authorized study site personnel may supply or administer IP. Only IP with appropriate expiry/retest dating may be dispensed.
- All IP must be stored in a secure, environmentally controlled and monitored (manual or automated) area in accordance with the labeled storage conditions and access must be limited to the investigator and authorized study site personnel.
- The investigator, institution or the head of the medical institution (where applicable) is responsible for accountability, reconciliation and record maintenance (i.e., receipt, reconciliation and final disposition records).
- Further guidance and instruction on final disposition of used and unused IP is provided in the pharmacy manual.

Refer to the pharmacy manual for detailed information regarding handling, storage and accountability of the IP.

6.3 Randomization

This is an open-label study. Participant enrollment and dispensation of IP will be performed via the interactive response technology (IRT) system. Specific IRT procedures will be described in the respective study manual.

6.3.1 Assignment and Allocation

Priority for enrollment will be given to the safety lead-in portion of the ASP0739 and pembrolizumab combination arm when both phase 2 single agent dose expansion and combination therapy safety lead-in are open.

If both single agent and combination therapy expansion cohorts are open for the same tumor type, participants will be randomized to either single agent or combination therapy cohorts and the randomization ratio will be based on the number of open slots still available at each cohort.

UNIQUE to Japan Sites:

Japanese participants will be only enrolled into the monotherapy arm of the dose expansion cohort.

6.4 Investigational Product Compliance

Dosing will take place in the clinical unit. The administration of IP will be supervised to ensure treatment compliance. The exact day and time of IP administration will be documented.

6.5 Dose Modification

Dose modifications of ASP0739 are not allowed at the individual participant level without prior consultation with the sponsor's medical monitor. Any participants who do not receive a subsequent dose within the scheduled time window in the schedules of assessments [[Table 1](#) and [Table 2](#)] can only resume treatment after discussion with the medical monitor.

Any participant experiencing a grade 3 AE after receiving a dose of ASP0739 may receive the subsequently scheduled dose of ASP0739 only after the observed grade 3 AE has resolved to grade 1; the subsequent dose of ASP0739 may be reduced by one dose level, either from 1×10^8 to 1×10^7 cells/dose or from 1×10^7 to 1×10^6 cells/dose.

Further treatment reduction/withdrawal can be implemented after discussion with the medical monitor, including for any clinically significant AEs affecting vital organs (e.g., cardiac events).

Refer to [[Sections 10.8](#) Appendix 8: Infusion Reaction Dose Modification and Treatment (Guidelines for ASP0739 and Pembrolizumab); [10.10](#) Appendix 10: Dose Modification and Toxicity Management for Immune-related Adverse Events; and [10.11](#) Appendix 11: Dose Modification and Toxicity Management of Infusion Reactions Related to Pembrolizumab] and the approved pembrolizumab package insert, summary of product characteristics monograph or local product information supplied by the manufacturer for the recommended treatment modifications for pembrolizumab.

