- The safety in the expansion cohorts will be monitored using Bayesian logistic model based on all DLT data obtained up to that time from both escalation cohorts and expansion cohorts and drug-related TEAEs leading to death. Safety monitoring with these models will be started when an expansion cohort is opened. Enrollment in expansion cohorts may be held based on the criteria described in [Section 9 Statistical Considerations].

The potential risk of irAEs and IRRs may be mitigated by closely monitoring participants' symptoms, signs and clinical laboratory test results to facilitate early identification and management, as per the guidelines in [Section 10.8 Appendix 8: Infusion Reaction Dose Modification and Treatment (Guidelines for ASP0739 and Pembrolizumab); Section 10.9 Appendix 9: Monitoring of Pembrolizumab Potential Immune-related Adverse Events; Section 10.10 Appendix 10: Dose Modification and Toxicity Management for Immune-related AEs; and Section 10.11 Appendix 11: Dose Modification and Toxicity Management of Infusion Reactions Related to Pembrolizumab]. The management of such toxicities should be based on institutional SOC and published guidelines, as appropriate based on investigator judgment, and on the protocol instructions regarding interruption or discontinuation of treatment.

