All PGx samples collected will be stored for a period of up to 15 years following study database lock. If there is no requirement for analysis, the whole blood sample will be destroyed after the planned storage period. The participant has the right to withdraw consent at any time. When a participant's withdraw notification is received, the PGx sample will be destroyed. The results of any PGx analysis conducted on a sample prior to its withdrawal will be retained at Astellas indefinitely unless otherwise specified by local regulation.

INFORMATION DISCLOSURE TO THE PARTICIPANTS

Exploratory PGx analysis may be conducted following the conclusion of the study, if applicable. The results of the PGx analysis will not be provided to any investigators or participants, nor can the results be requested at a later date. Any information that is obtained from the PGx analysis will be the property of Astellas.

10.8 Appendix 8: Infusion Reaction Dose Modification and Treatment (Guidelines for ASP0739 and Pembrolizumab)

Table 14 Infusion Reaction Dose Modification and Treatment (Guidelines for ASP0739 and Pembrolizumab)

NCI-CTCAE Grade	Treatment	Premedication at Subsequent Dosing
Grade 1 Mild reaction; infusion interruption not indicated; intervention not indicated	
Increase monitoring of vital signs as medically indicated until the participant is deemed medically stable in the opinion of the investigator.	None

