Grade 2 Requires therapy or infusion interruption but responds promptly to symptomatic treatment (e.g., antihistamines, NSAIDs, narcotics, intravenous fluids); prophylactic medications indicated for \leq 24 hours.	
Stop Infusion.Additional appropriate medical therapy may include but is not limited to:
Intravenous fluidsAntihistaminesNSAIDsAcetaminophenNarcoticsIncrease monitoring of vital signs as medically indicated until the participant is deemed medically stable in the opinion of the investigator.If symptoms resolve within 1 hr of stopping drug infusion, the infusion may be restarted at 50% of the original infusion rate (e.g., from 100 mL/hr. to 50 mL/hr.). Otherwise, dosing will be held until symptoms resolve and the participant should be premedicated for the next scheduled dose. 
Participants who develop grade 2 toxicity despite adequate premedication should be permanently discontinued from further treatment (pembrolizumab only)
	
Pembrolizumab only: Participant may be premedicated 1.5 hours (\pm 30 min) prior to infusion of pembrolizumab with: Diphenhydramine 50 mg po (or equivalent dose of antihistamine). Acetaminophen 500 to 1000 mg po (or equivalent dose of analgesic).
 
Contact the study medical monitor regarding ASP0739 dose management

Table continued on next page

NCI-CTCAE Grade	Treatment	Premedication at Subsequent Dosing

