Grades 3 or 4 Grade 3: Prolonged (i.e., not rapidly responsive to symptomatic medication and/or brief interruption of infusion); recurrence of symptoms following initial improvement; hospitalization indicated for other clinical sequelae (e.g., renal impairment, pulmonary infiltrates) Grade 4: Life-threatening; pressor or ventilator support indicated	
 Stop Infusion. Additional appropriate medical therapy may include, but is not limited to: 
 Epinephrine* Intravenous fluids Antihistamines NSAIDs Acetaminophen Narcotics Oxygen Pressors Corticosteroids Increase monitoring of vital signs as medically indicated until the participant is deemed medically stable in the opinion of the investigator. Once the participant has been stabilized, collect blood for cytokine/chemokine panel (ad hoc collection for shipment to central lab). If the reaction is suggestive of anaphylaxis, collect blood (standard red top tube) for serum total tryptase level (levels typically peak within 3 hours after the onset of symptoms). Serum should be frozen if the assay cannot be performed promptly at the local laboratory. Hospitalization may be indicated. 
* In cases of anaphylaxis, epinephrine should be used immediately. Participant is permanently discontinued from further study drug treatment.
	Any grade 4 hypersensitivity reaction/anaphylaxis, study treatment should be discontinued

Appropriate resuscitation equipment should be available at the bedside and a physician readily available during the period of drug administration. For further information, please refer to the Common Terminology Criteria for Adverse Events v5.0 (CTCAE) at <http://ctep.cancer.gov>.

hr: hour; NCI: National Cancer Institute; NSAID: non-steroidal anti-inflammatory drug; po: by mouth

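### Section 6.5 allows ASP0739 re-dosing after any resolved grade 3 AE without excepting infusion reactions, for which Table 14 stops study drug permanently

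*Protocol*

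**What the plan says.** **Section 6.5 (Dose Modification).** After any grade 3 AE following ASP0739, the participant "may receive the subsequently scheduled dose of ASP0739 only after the observed grade 3 AE has resolved to grade 1". The same sentence adds that "the subsequent dose of ASP0739 may be reduced by one dose level", from 1×10^8 to 1×10^7 or from 1×10^7 to 1×10^6 cells. No type of AE is excepted. The section requires prior consultation with the medical monitor for a dose modification. Its last sentence cites Appendices 8, 10 and 11 and the product label "for the recommended treatment modifications for pembrolizumab".

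**Appendix 8, Table 14.** The title reads "Infusion Reaction Dose Modification and Treatment (Guidelines for ASP0739 and Pembrolizumab"), so it reaches single-agent participants. The relevant entries are:

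- Grade 2 row, treatment column: "Participants who develop grade 2 toxicity despite adequate premedication should be permanently discontinued from further treatment (pembrolizumab only"). The closing bracket confines that stop to one agent. The right-hand column of this row refers ASP0739 dosing to the medical monitor.
- Grades 3 or 4 row, treatment column: "Participant is permanently discontinued from further study drug treatment". No agent is singled out. In the text as supplied, this sentence comes straight after the note on epinephrine for anaphylaxis.
- Grades 3 or 4 row, right-hand column (premedication at later doses): "Any grade 4 hypersensitivity reaction/anaphylaxis, study treatment should be discontinued". Grade 3 is not mentioned.

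**Section 2.3.2 (Risk Mitigation).** "The potential risk of irAEs and IRRs may be mitigated by closely monitoring" participants, with identification and management of these reactions referred to Appendix 8 among others.

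**The concern.** Section 6.5 is where a site would look first to decide whether a participant may have the next ASP0739 dose. For grade 3 events it gives a single condition, resolution to grade 1. An infusion reaction often resolves quickly, so it can meet that condition well before the next 28-day cycle. Table 14 ends study drug for the same event. Nothing in Section 6.5 sends the reader to Table 14 for ASP0739, because the pointer is worded for pembrolizumab.

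The consequence is for participant safety and for consistent handling across sites. Two sites could each follow a part of the protocol and treat the same severe reaction to a first-in-human cell product differently. No endpoint, sample size, power or error rate is involved.

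**Working it through.** There is no figure in the plan to reproduce. The check is to follow one case through every rule that could apply.

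**Case.** A single-agent participant has a grade 3 infusion reaction at cycle 1. It falls to grade 2 or lower within 72 hours, reaches grade 1 before cycle 2, and meets no other DLT criterion.

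| Rule | What it gives for this case |
|---|---|
| Section 4.1, single-agent DLT list and stopping rules | No stop. The 72-hour rule catches only non-hematological events of grade 3 or higher that have not come down to grade 2 or lower in time. The combination list counts an infusion-related reaction that forces the infusion to be discontinued; the single-agent list has no such item. |
| Section 6.5 | The condition is met, so the next dose may be given in full or one level lower. A full dose on schedule is not a dose modification, so this section's requirement to consult the monitor is not triggered. |
| Table 14, Grades 3 or 4, treatment column | No further study drug, read on the row heading. |
| Table 14, Grades 3 or 4, right-hand column | A stop for grade 4 hypersensitivity or anaphylaxis; nothing for grade 3. |
| Section 8.1 | No stop specific to infusion reactions; an AE ends treatment where the investigator judges that continuing is not in the participant's interest. |
| Section 7 and Appendix 10 | Discussion with the sponsor for immediate safety concerns, and monitor contact for immune-related reactions. Neither says which re-dosing rule applies. |

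**Precedence.** Section 2.3.2 refers infusion reactions to Appendix 8, and Table 14 is the narrower rule. Both favor Table 14. No sentence in Section 6.5 or Appendix 8 states it.

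**Cases outside the gap.** Section 6.5's sentence covers grade 3 only, so it says nothing against a stop at grade 4. A grade 3 reaction that does not come down to grade 2 or lower within 72 hours is stopped under Section 4.1.

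**Size for one participant.**

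- Next dose at 1×10^7 cells: 0 (Table 14), 1×10^6 (reduced) or 1×10^7 (full).
- Next dose at 1×10^8 cells: 0, 1×10^7 or 1×10^8.
- The optional reduction is 10-fold: 10^8 / 10^7 = 10.
- Later doses at stake after a cycle 1 reaction: cycle 2 alone, 2 − 1 = 1. With clinical benefit, cycles 2 to 4, 4 − 1 = 3. With partial response or stable disease, cycles 2 to 6, 6 − 1 = 5 (Table 1, footnotes b and c).

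The documents give no frequency for grade 3 infusion reactions, so the number of participants affected cannot be estimated.

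**The case against.** The strongest reply is that the two rules are compatible. Section 6.5 says a participant may be dosed only after resolution. That is a necessary condition, not a right to the dose, and stopping under Table 14 breaches nothing in it. Section 2.3.2 directs infusion-reaction management to Appendix 8, and Section 6.5 itself cites that appendix by a title that names ASP0739. The Grade 2 row separates the agents where separation was wanted, so the unrestricted stop in the next row naturally covers both. Since grade 2 already brings in the monitor for ASP0739, a full dose after grade 3 without discussion is an unlikely reading. Section 7 also asks for immediate safety concerns to be discussed with the sponsor, so as to decide whether treatment continues.

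Most of this stands. It shows what was probably intended, and it rules out calling the texts flatly contradictory. It does not remove the gap: a site that applies Section 6.5 as written may re-dose a participant whom Table 14 stops, and no text tells it that Table 14 takes precedence.

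The reply is also right on two details. The right-hand column concerns premedication, and its silence on grade 3 is not a contrary instruction. The position of the stop sentence after the anaphylaxis note may be an effect of text extraction, so little should rest on it.

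**Conclusion.** The concern holds in a limited form. Section 6.5 lacks an infusion-reaction exception and does not defer to Table 14 for ASP0739, although Table 14 is probably meant to govern. The case affected is a single-agent grade 3 infusion reaction that settles within 72 hours and is not otherwise a DLT. This assumes that the treatment-column stop applies to the whole Grades 3 or 4 row, as the row heading indicates.

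A reader might infer more, and the documents do not support it:

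- *That the protocol directs re-dosing after a grade 3 infusion reaction.* Section 6.5 only permits it, subject to a condition.
- *That Table 14 contradicts itself by allowing dosing after grade 3.* The right-hand column names grade 4 and is silent on grade 3.
- *That participants were harmed or left without oversight.* Section 2.3.1.1 reports no DLTs or safety concerns in the 4 participants treated at 1×10^7 cells by 06 May 2022, and Sections 7 and 8.1 provide general safeguards.

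The SAP Introduction records early termination with no combination treatment, so practical impact is small. The change is still worth making because it concerns participant safety and costs almost nothing.

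**What to change.** 1. In Section 6.5, add to the grade 3 sentence: 'except infusion reactions, for which Table 14 (Appendix 8) governs ASP0739 re-dosing'.
2. In the right-hand column of Table 14's Grades 3 or 4 row, state: 'No subsequent dosing: study drug is permanently discontinued after a grade 3 or 4 infusion reaction'. In the treatment column, set that stop apart from the anaphylaxis and epinephrine note.

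Keep the existing stop on study drug. Do not narrow it to the agent judged to have caused the reaction. In combination participants ASP0739 may follow pembrolizumab by as little as 1 hour (Section 6.1.1), so that wording would add a causality judgment and could loosen the stop.

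The cost is one clause and one table row, with no added visits, data or participants. The small downside is that a participant whose grade 3 reaction resolves quickly loses the later ASP0739 doses. If Table 14 was always meant to govern, those doses were not available anyway.

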6.6 Continued Access to Investigational Product After the End of the Study

ASP0739 will be given up to a maximum of 6 cycles. ASP0739 and pembrolizumab will not be made available after conclusion of the study to participants who are still receiving and benefitting from study treatment in countries where the product does not have marketing approval and is not commercially available, as the treatment with ASP0739 does not have authorization to be administered after the study is complete.

6.7 Treatment of Overdose

In the event of suspected ASP0739 overdose, the participant should receive supportive care and monitoring. The medical monitor/expert should be contacted as applicable.

For this study, an overdose of pembrolizumab will be defined as any dose of 1000 mg or ≥ 2.5 times the indicated dose.

No specific information is available on the treatment of overdose of pembrolizumab. In the event of overdose, the participant should be observed closely for signs of toxicity. Appropriate supportive treatment should be provided if clinically indicated.

In the event of suspected pembrolizumab overdose, refer to the approved package insert, summary of product characteristics or local product information supplied by the manufacturer.

Refer to [Section 10.3.7 Reporting Procedures for Special Situations] for reporting requirements for suspected overdose or other medication error.

6.8 Concomitant Therapy

The following treatments are prohibited during the study:

- The use of systemic steroids (> 30 mg per day of hydrocortisone or > 10 mg per day of prednisone or equivalent) is not allowed during study treatment unless needed to manage AEs related to study treatment. The use of topical, ocular, intra-articular, intranasal, and inhalational corticosteroids (with minimal systemic absorption) is allowed. Physiologic replacement doses of systemic corticosteroids (≤ 30 mg per day of hydrocortisone or ≤ 10 mg per day of prednisone or equivalent) are permitted. Corticosteroids for prophylaxis (e.g., contrast dye allergy) or for brief treatment of conditions not related to study treatment (e.g., delayed-type hypersensitivity reaction caused by a contact allergen) is also allowed. Corticosteroids to manage irAEs are permitted.
- Immunosuppressive agents including but not limited to, high dose steroids, mammalian target of rapamycin inhibitors (e.g., rapamycin) or mycophenolate mofetil.
- Investigational agents other than ASP0739 and pembrolizumab.
- Any other cancer directed therapies are prohibited during the study with ASP0739 and ASP0739 and pembrolizumab, including chemotherapy, biologic therapy, radiation therapy or surgery.
 - *Palliative (limited field) radiation therapy:* for bone metastases is allowed. Study treatment should be interrupted during radiation therapy. The use of bisphosphonates and receptor activator of nuclear factor kappa-B ligand inhibitors for bone metastases is allowed if initiated prior to screening.
- Vaccines: Live vaccines are prohibited while the participant is receiving study treatment and for 30 days after last dose of study treatment. Examples of live vaccines include, but are not limited to, the following: measles, mumps, rubella, chicken pox, yellow fever, seasonal flu, H1N1 flu, rabies, bacillus Calmette-Guérin and typhoid vaccine.
 - COVID-19 prevention is allowed if non-live vaccines are to be used. In cases where a live vaccine is needed for COVID-19 prevention, please contact the medical monitor for discussion.

Refer to [Section 10.5 Appendix 5: List of Excluded Concomitant Medications] for a detailed list of drug classes and/or specific medications that are prohibited during participation in the study.

7 STUDY PROCEDURES AND ASSESSMENTS

- Study procedures and their timing are summarized in the schedules of assessments [Table 1 through Table 3]. Adherence to the study design requirements, including those specified in the schedule of assessments, is essential and required for study conduct. Prospective protocol waivers or exemptions are not allowed.
- Any change, divergence or departure from the study design or procedures identified in the protocol is considered a protocol deviation. All deviations from the protocol are to be recorded.
- Immediate safety concerns should be discussed with the sponsor immediately upon occurrence or awareness to determine if the participant should continue or discontinue study treatment.
- All screening evaluations must be completed and reviewed to confirm that potential participants meet all eligibility criteria. The investigator will maintain a screening log to record details of all participants screened and to confirm eligibility or record reasons for screening failure, as applicable.
- Procedures conducted as part of the participant's routine clinical management (e.g., imaging, blood count) and obtained before signing of the ICF may be utilized for screening or baseline purposes provided the procedures met the protocol-specified criteria and were performed within the time frame defined in the schedule of assessments.

7.1 Efficacy Assessments

Disease response and progression will be evaluated in this study using the RECIST v1.1 and iRECIST criteria as assessed by independent central review and investigator.

Tumor assessments will be performed at screening and every 8 weeks (\pm 1 week) from C1D1 until confirmed disease progression by iRECIST (iCPD). Scans will be read on site and also submitted in digital format for independent central review. Procedures for independent imaging central review will be described in a separate imaging charter. The assessment will include tumor measurements for target lesions, non-target lesions, and assessment for any new lesions. An overall assessment will be characterized for time point evaluation.

Computed tomography (CT) or magnetic resonance imaging (MRI) scans are preferred for this study and to ensure comparability, the same technique (CT/MRI) used at screening should be utilized throughout the study. The same method should be employed and assessed by the same individual on each occasion, when possible. Imaging should include chest, abdomen and pelvis as well as any other anatomical region appropriate for the participant's disease.

Imaging should be done every 8 weeks from C1D1 regardless of treatment interruption or delays and through the follow-up period as applicable. Scans performed prior to informed

consent as SOC are acceptable as screening scans if done within 28 days prior to C1D1. If a biopsy of a target lesion is performed, the baseline scan should be repeated, if possible.

Confirmatory scans for complete response (CR) or PR should be done at least 4 weeks after the date of the scan that CR or PR was first observed. Confirmatory scans for progressive disease (PD) must occur at least 4 weeks after the date of the scan that PD was first observed but no longer than 8 weeks.

